#### **6.2.2.10 Permitted study drug adjustments**

For patients who may require dose adjustments because of concomitant medication, please refer to [Section 6.1.3](#). For patients who are unable to tolerate the protocol-specified dosing schedule, dose adjustments are permitted in order to allow the patient to continue study drug. The following guidelines should be followed. These changes must be recorded on the Dosage Administration Record eCRF. If treatment is interrupted due to toxicity, study drug should not be resumed until recovery to Grade  $\leq 1$ . Study drug can then be reintroduced at the initial dose or a lower dose level depending on the toxicity type and Grade (see [Table 6-9](#), [Table 6-10](#), [Table 6-11](#)).

These changes must be recorded on the Dosage Administration Record eCRF.

**Table 6-9 Dose reduction steps for everolimus**

Dose reduction*			
	Starting dose level	Dose level – 1	Dose level - 2
Everolimus	10 mg daily	5 mg daily	5 mg every other day**

\*Dose reduction should be based on the worst toxicity demonstrated at the last dose received.  
\*\*Dose reduction below 5 mg every other day is not allowed. Treatment must be discontinued.

Management of severe or intolerable adverse drug reactions (ADRs) may require temporary dose interruption (with or without dose reduction) or discontinuation of everolimus therapy. If dose reduction is required, the suggested dose is approximately 50% lower than the daily dose

previously administered. For dose reductions below the lowest available tablet strength, alternate day dosing should be considered.

**Table 6-10** and **Table 6-11** summarize the recommendations for dose interruption, reduction, or discontinuation of everolimus in the management of ADRs. General management recommendations are also provided as applicable. Clinical judgment of the treating physician should guide the management plan of each patient based on individual benefit/risk assessment.

**Table 6-10 Dosing guidelines for study drug-related non-hematologic toxicities**

Adverse drug reaction	Severity	Everolimus dose adjustment and management recommendations
Non-infectious pneumonitis	Grade 1  Asymptomatic, radiographic findings only	No dose adjustment required.  Initiate appropriate monitoring.
	Grade 2  Symptomatic, not interfering with ADL 	Consider interruption of therapy, rule out infection and consider treatment with corticosteroids until symptoms improve to Grade $\leq 1$ .  Re-initiate everolimus at a lower dose.  Discontinue treatment if failure to recover within 4 weeks.
	Grade 3  Symptomatic, interfering with ADL 	Interrupt everolimus until symptoms resolve to Grade $\leq 1$ .  Rule out infection and consider treatment with corticosteroids.
	O 2 indicated	Consider re-initiating everolimus at a lower dose.  If toxicity recurs at Grade 3, consider discontinuation.
	Grade 4  Life-threatening, ventilatory support indicated	Discontinue everolimus, rule out infection, and consider treatment with corticosteroids.

Adverse drug reaction	Severity	Everolimus dose adjustment and management recommendations
Stomatitis	Grade 1  Minimal symptoms, normal diet	No dose adjustment required.  Manage with non-alcoholic or salt water (0.9%) mouthwash several times a day.
	Grade 2  Symptomatic but can eat and swallow modified diet	Temporary dose interruption until recovery to Grade $\leq 1$ .  Re-initiate everolimus at the same dose.  If stomatitis recurs at Grade 2, interrupt dose until recovery to Grade $\leq 1$ . Re-initiate everolimus at a lower dose.  Manage with topical analgesic mouth treatments (e.g., benzocaine, butyl aminobenzoate, tetracaine hydrochloride, menthol or phenol) with or without topical corticosteroids (i.e. triamcinolone oral paste). 
	Grade 3  Symptomatic and unable to adequately eat or hydrate orally	Temporary dose interruption until recovery to Grade $\leq 1$ .  Re-initiate everolimus at a lower dose.  Manage with topical analgesic mouth treatments (e.g., benzocaine, butyl aminobenzoate, tetracaine hydrochloride, menthol or phenol) with or without topical corticosteroids (i.e. triamcinolone oral paste). 
	Grade 4  Symptoms associated with life-threatening Consequences	Discontinue everolimus and treat with appropriate medical therapy.
Other non-hematologic toxicities  (excluding metabolic events)	Grade 1	If toxicity is tolerable, no dose adjustment required.  Initiate appropriate medical therapy and monitor.
	Grade 2	If toxicity is tolerable, no dose adjustment required.  Initiate appropriate medical therapy and monitor.  If toxicity becomes intolerable, temporary dose interruption until recovery to Grade $\leq 1$ . Re-initiate everolimus at the same dose.  If toxicity recurs at Grade 2, interrupt everolimus until recovery to Grade $\leq 1$ . Re-initiate everolimus at a lower dose.
	Grade 3	Temporary dose interruption until recovery to Grade $\leq 1$ .  Initiate appropriate medical therapy and monitor.  Consider re-initiating everolimus at a lower dose.  If toxicity recurs at Grade 3, consider discontinuation.
	Grade 4	Discontinue everolimus and treat with appropriate medical therapy.

Adverse drug reaction	Severity	Everolimus dose adjustment and management recommendations
Metabolic events (e.g. hyper-glycemia, dys-lipidemia)	Grade 1	No dose adjustment required. Initiate appropriate medical therapy and monitor.
	Grade 2	No dose adjustment required. Manage with appropriate medical therapy and monitor.
	Grade 3	Temporary dose interruption. Re-initiate everolimus at a lower dose. Manage with appropriate medical therapy and monitor.
	Grade 4	Discontinue everolimus and treat with appropriate medical therapy.

 Severity Grade description: 1 = mild symptoms; 2 = moderate symptoms; 3 = severe symptoms; 4 = life-threatening symptoms.

 If dose reduction is required, the suggested dose is approximately 50% lower than the dose previously administered.

 Activities of daily living (ADL)

 Avoid using agents containing alcohol, hydrogen peroxide, iodine, and thyme derivatives in management of stomatitis as they may worsen mouth ulcers.

**Table 6-11 Dosing guidelines for study drug-related hematologic toxicities**

Adverse event	Severity 	Everolimus Dose Adjustment
Platelet count decreased (Thrombocytopenia)	Grade 1 (<LLN-75.0x10  /L)	No dose adjustment required.
	Grade 2 (<75.0-50.0x10  /L)	Temporary dose interruption until recovery to Grade $\leq$ 1. Re-initiate everolimus at the same dose.
	Grade 3 (<50.0-25.0x10  /L)	Temporary dose interruption until recovery to Grade $\leq$ 1. Re-initiate everolimus at a lower dose.
	Grade 4 (<25.0x10  /L)	Temporary dose interruption until recovery to Grade $\leq$ 1. Re-initiate everolimus at a lower dose.
Neutrophil count decreased (Neutropenia)	Grade 1 (<LLN-1.5x10  /L)	No dose adjustment required.
	Grade 2 (<1.5-1.0x10  /L)	No dose adjustment required.
	Grade 3 (<1.0-0.5x10  /L)	Temporary dose interruption until recovery to Grade $\leq$ 2 (ANC $\geq$ 1.0x10  /L). Re-initiate everolimus at the same dose.
	Grade 4 (<0.5x10  /L)	Temporary dose interruption until recovery to Grade $\leq$ 2 (ANC $\geq$ 1.0x10  /L). Re-initiate everolimus at a lower dose.
Febrile neutropenia	Grade 3 (ANC <1.0x10  /L with single temperature $>$ 38.3° C (101°F) or sustained temperature $\geq$ 38°C (100.4°F) for $>$ 1h)	Temporary dose interruption until recovery to Grade $\leq$ 2 (ANC $\geq$ 1.25x10  /L) and no fever. Re-initiate everolimus at a lower dose.
	Grade 4 (Life-threatening consequences; urgent intervention indicated)	Discontinue everolimus.
Any hematologic toxicity requiring study drug interruption for $>$ 28 days		Discontinue everolimus.

 Grading based on National Cancer Institute (NCI) Common Terminology Criteria for Adverse Events (CTCAE) v4.03

## 6.3 Patient numbering, treatment assignment or randomization

### 6.3.1 Patient numbering

Each patient is identified in the study by a Patient Number that is assigned when the patient is first enrolled for screening and is retained as the primary identifier for the patient throughout her entire participation in the trial. The Patient No. consists of the Center Number (Center No.) (as assigned by Novartis to the investigative site) with a sequential patient number suffixed to it, so that each subject is numbered uniquely across the entire database. Upon signing the informed consent form, the patient is assigned to the next sequential Patient Number.

### 6.3.2 Treatment assignment for oral stomatitis therapy

Upon diagnosis of stomatitis, patients in countries where the alcohol-free 0.5mg/5ml dexamethasone oral solution is commercially available, will be randomized in 1:1 ratio to take either 0.5mg/5ml dexamethasone mouth rinse or standard of care at the patient's center. The assignment of a patient to a particular cohort will be coordinated by the sponsor. A randomization list will be produced by or under the responsibility of Novartis Drug Supply Management and the Biostatistician. The randomization list will be reviewed by a Biostatistics Quality Assurance Group and locked by them after approval.

During the Extension Phase, standard of care at the patient's site as recommended by the investigator to treat stomatitis will be followed.

### 6.3.3 Treatment blinding

This is an open-label trial, treatment will not be blinded.

## 6.4 Study drug preparation and dispensation

The investigator or responsible site personnel must instruct the patient or caregiver to take the study drugs as per protocol. Study drug(s) will be dispensed to the patient by authorized site personnel only. All dosages prescribed to the patient and all dose changes during the study must be recorded on the Dosage Administration Record CRF.

**Table 6-12 Preparation and dispensing**

Study treatments	Dispensing	Preparation
Everolimus (RAD001)	Tablets including instructions for administration are dispensed by study personnel on an outpatient basis. Patients will be provided with adequate supply of study treatment for self-administration at home until at least their next scheduled study visit.	Refer to local product information
Letrozole	Oral tablets	Refer to local product information
Exemestane	Oral tablets	Refer to local product information
dexamethasone	Oral solution	Refer to local product information

### 6.4.1 Study drug packaging and labeling

Everolimus can be provided with locally available commercial material or centrally as needed. It will be supplied and labeled accordingly to comply with the legal requirements of local Health Authority regulations in each country. Medication labels for the centrally provided everolimus (RAD001), under the responsibility of Novartis DSM will comply with the legal regulations of each country and be printed in local language. Everolimus (RAD001) will be open-label to allow patients to take medication at home. For countries where the study medications are supplied by Novartis DSM, the supplies will be sent as open-label bulk supply. The storage conditions for study drug will be described on the medication label. Commercially available letrozole and exemestane will be supplied to sites or prescribed to

patients in accordance with local regulations in participating countries. The storage conditions will be described on the medication label.

**Table 6-13 Packaging and labeling**

Study treatments	Packaging	Labeling (and dosing frequency)
Everolimus (RAD001)	Tablets in blister packs	Labeled as Everolimus (RAD001); 2-5mg tablets to be taken orally
Letrozole	Refer to local product information	2.5mg tablets to be taken orally. Refer to local product information
Exemestane	Refer to local product information	25mg tablet to be taken orally. Refer to local product information
dexamethasone (for patients randomized to dexamethasone treatment)	Refer to local product information	0.5mg/5ml Oral solution to be swished and expectorated 3 times per day for duration of stomatitis. Refer to local product information for additional details

#### **6.4.2 Drug supply and storage**

Study treatments must be received by designated personnel at the study site, handled and stored safely and properly, and kept in a secured location to which only the investigator and designated site personnel have access. Upon receipt, the study treatment should be stored according to the instructions specified on the drug labels.

**Table 6-14 Supply and storage of study treatments**

Study treatments	Supply	Storage
Everolimus (RAD001)	Locally or centrally supplied by Novartis as needed	Refer to study treatment label
Letrozole	Locally supplied by Novartis as needed or by prescription in applicable countries	Refer to local product information
Exemestane	Locally supplied by Novartis as needed or by prescription in applicable countries	Refer to local product information
0.5mg/5ml dexamethasone	Supplied via prescription in countries where it is commercially available	Refer to local product information.

#### **6.4.3 Study drug compliance and accountability**

##### **6.4.3.1 Study drug compliance**

Study drug compliance will be assessed by the investigator and/or study personnel using pill counts at each patient visit and information provided by the patient and/or caregiver will be captured in the Drug Accountability Form. This information must be captured in the source document at each patient visit.

#### **6.4.3.2 Study drug accountability**

The investigator or designee must maintain an accurate record of the shipment and dispensing of study drug in a drug accountability log. Drug accountability will be noted by the field monitor during site visits and at the completion of the study. Patients will be asked to return all unused study drug and packaging on a regular basis, at the end of the study or at the time of study treatment discontinuation.

At study close-out, and, as appropriate during the course of the study, the investigator will return all used and unused study drug, packaging, drug labels, and a copy of the completed drug accountability log to the Novartis monitor or to the Novartis address provided in the investigator folder at each site.

#### **6.4.3.3 Handling of other study treatment**

Storage conditions for letrozole, exemestane and dexamethasone will be described on the medication label.

#### **6.4.4 Disposal and destruction**

The study drug supply can be destroyed at the local Novartis facility, Drug Supply group or third party, as appropriate.

### **7 Visit schedule and assessments**

#### **7.1 Study flow and visit schedule**

[Table 7-1](#), [Table 7-2](#) and [Table 7-3](#) lists all of the assessments and indicates with an “X”, the visits when they are performed. All data obtained from these assessments must be supported in the patient’s source documentation. No CRF will be used as a source document.

**Table 7-1 Visit evaluation schedule (Core Phase: First line treatment)**

	Category	Reference to Section	Screening/ Baseline	Cycles 1 cycle = 28 days*				End of treatment (EoT) for first line treatment	28 Day Safety Follow up*	Study Evaluation completion*	Survival follow up**	Post Treatment Evaluations
Cycle Number				C1	C2	C3	Subsequent cycles					
Visit Number			1	2	3	4	5,6,7...	777	501	778		
Day of cycle			-28 to -1	1	1	1	1	Last dose + ≤15 days	Last dose + 28 days			
Obtain Informed Consent	D	7.1.1.1.	X									
Eligibility checklist	S	7.1.1.1.	X									
Patient history:												
Demography	D	7.1.1.4.	X									
Inclusion/exclusion criteria	S/D	5.2. 5.3.	X									
Relevant medical history/current medical conditions	D	7.1.1.4.	X									
Diagnosis and extent of cancer	D	7.1.1.4.	X									
Prior antineoplastic therapy	D	7.1.1.4.	X									
Prior/concomitant medications	D	7.1.1.4.	X	Continuous during the study up to 28 days after last treatment								
Physical examination:												
Physical examination	S	7.2.2.1.	X	X	X	X	Day 1 of subsequent cycles	X				

	Category	Reference to Section	Screening/ Baseline	Cycles 1 cycle = 28 days*				End of treatment (EoT) for first line treatment	28 Day Safety Follow up*	Study Evaluation completion*	Survival follow up**	Post Treatment Evaluations
Cycle Number				C1	C2	C3	Subsequent cycles					
Visit Number			1	2	3	4	5,6,7...	777	501	778		
Day of cycle			-28 to -1	1	1	1	1	Last dose + ≤15 days	Last dose + 28 days			
ECOG Performance status	D	7.2.2.4.	X	X	X	X	Day 1 of subsequent cycles	X				
Height	D	7.2.2.3.	X									
Weight	D	7.2.2.3.	X	X	X	X	Day 1 of subsequent cycles	X				
Vital signs	D	7.2.2.2.	X	X	X	X	Day 1 of subsequent cycles	X				
ECG	D	7.2.2.6.1.	X	As clinically indicated								
Pulmonary function test (PFTs)	D	7.2.2.7.	As clinically indicated									
Laboratory assessments:		7.2.2.5.										
Hematology	D	7.2.2.5.1.	X	X	X	X	Day 1 of subsequent cycles	X				
Chemistry	D	7.2.2.5.2.	X	X	X	X	Day 1 of subsequent cycles	X				
Coagulation	D	7.2.2.5.3.	X	As clinically indicated								

	Category	Reference to Section	Screening/ Baseline	Cycles 1 cycle = 28 days*				End of treatment (EoT) for first line treatment	28 Day Safety Follow up*	Study Evaluation completion*	Survival follow up**	Post Treatment Evaluations
Cycle Number				C1	C2	C3	Subsequent cycles					
Visit Number			1	2	3	4	5,6,7...	777	501	778		
Day of cycle			-28 to -1	1	1	1	1	Last dose + ≤15 days	Last dose + 28 days			
Hepatitis screening and monitoring (if applicable)	D	7.2.2.5.4. 7.2.2.5.5.	X									
Urinalysis	D	7.2.2.5.6.	X	As clinically indicated								
Imaging:		7.2.1.										
CT or MRI for chest, abdomen, pelvis	D	7.2.1.	X			X	Every 8 weeks	X only for patients discontinuing for reasons other than documented PD, lost to follow up and death				X
CT or MRI for Brain	D	7.1.1.4.	X	As clinically indicated								
Bone scan or skeletal survey	D	7.2.1.	X			X	Every 8 weeks					
If baseline bone scan positive perform X-ray, CT or MRI	D	7.2.1.	X			X	Every 8 weeks	X only for patients discontinuing for reasons other than documented PD, lost to follow up and death				

	Category	Reference to Section	Screening/ Baseline	Cycles 1 cycle = 28 days*				End of treatment (EoT) for first line treatment	28 Day Safety Follow up*	Study Evaluation completion*	Survival follow up**	Post Treatment Evaluations
Cycle Number				C1	C2	C3	Subsequent cycles					
Visit Number			1	2	3	4	5,6,7...	777	501	778		
Day of cycle			-28 to -1	1	1	1	1	Last dose + ≤15 days	Last dose + 28 days			
Safety:			7.2.2.									
Adverse events	D	7.2.2.			Continuous during the study, up to 28 days after the last treatment				X			
Patient reported Outcomes – OSDQ		7.2.6.			Complete OSDQ daily during every episode of oral stomatitis.							
Everolimus administration	D	6.1.			Daily dosing							
Letrozole administration	D	6.1.			Daily dosing for FIRST LINE TREATMENT ONLY							
Study Evaluation Completion	D	7.1.6.1.							X			
Survival Follow-up	D	7.1.6.2.								X		
Antineoplastic therapies since discontinuation of study treatment	D	5.							X			X

	Category	Reference to Section	Screening/ Baseline	Cycles 1 cycle = 28 days*				End of treatment (EoT) for first line treatment	28 Day Safety Follow up*	Study Evaluation completion*	Survival follow up**	Post Treatment Evaluations
Cycle Number				C1	C2	C3	Subsequent cycles					
Visit Number			1	2	3	4	5,6,7...		777	501	778	
Day of cycle			-28 to -1	1	1	1	1		Last dose + ≤15 days	Last dose + 28 days		

**Table 7-2 Visit evaluation schedule (Core Phase: Second-line treatment)**

	Category	Reference to Section	Cycles* 1 cycle = 28 days				End of treatment (EoT) for second line treatment	28 Day Safety Follow up*	Study Evaluation Completion*	Survival follow up**	Post Treatment Evaluations
Cycle Number			Cycle 101	C102	C103	Subsequent cycles					
Visit Number			102	103	104	105, 106, 107...	779	501	778		
Day of cycle			Day 1 of each cycle				Last dose + ≤15 days	Last dose + 28 days			
Inclusion/exclusion criteria re-examination	S/D	7.1.3.	X								
Concomitant medications	D	7.1.1.4.	Continuous during the study up to 28 days after last treatment								
Physical examination	S	7.2.2.1.	Day 1 of each cycle				X				
ECOG Performance status	D	7.2.2.4.	Day 1 of each cycle				X				
Weight	D	7.2.2.3.	Day 1 of each cycle				X				
Vital signs	D	7.2.2.2.	Day 1 of each cycle				X				
ECG	D	7.2.2.6.1.	As clinically indicated								
Pulmonary function test (PFTs)	D	7.2.2.7.	As clinically indicated								
Laboratory assessments:		7.2.2.5.									
Hematology	D	7.2.2.5.1.	Day 1 of each cycle				X				
Chemistry	D	7.2.2.5.2.	Day 1 of each cycle				X				
Coagulation	D	7.2.2.5.3.	As clinically indicated								
Urinalysis	D	7.2.2.5.6.	As clinically indicated								

	Category	Reference to Section	Cycles* 1 cycle = 28 days				End of treatment (EoT) for second line treatment	28 Day Safety Follow up*	Study Evaluation Completion*	Survival follow up**	Post Treatment Evaluations		
Cycle Number			Cycle 101	C102	C103	Subsequent cycles							
Visit Number			102	103	104	105, 106, 107...	779	501	778				
Day of cycle			Day 1 of each cycle				Last dose + ≤15 days	Last dose + 28 days					
Hepatitis testing	D	7.2.2.5.4. 7.2.2.5.5.											
Imaging:		7.2.1.											
CT or MRI for Brain	D	7.1.1.4.	As clinically indicated										
CT or MRI for chest, abdomen, pelvis	D	7.2.1.		X	Every 8 weeks		X only for patients discontinuing for reasons other than documented PD, lost to follow up and death				X		
If bone scan positive perform X-ray, CT or MRI	D	7.2.1.		X	Every 8 weeks		X only for patients discontinuing for reasons other than documented PD, lost to follow up and death						
Safety:		7.2.2.											
Adverse events	D	7.2.2.	Continuous during the study, up to 28 days after the last treatment				X						
Patient reported Outcomes – OSDQ		7.2.6.	Complete OSDQ daily during every episode of oral stomatitis.										
Everolimus administration	D	6.1.	Daily dosing										
Exemestane administration	D	6.1.	Daily dosing after initial progression for SECOND-LINE TREATMENT ONLY										

	Category	Reference to Section	Cycles* 1 cycle = 28 days				End of treatment (EoT) for second line treatment	28 Day Safety Follow up*	Study Evaluation Completion*	Survival follow up**	Post Treatment Evaluations
Cycle Number			Cycle 101	C102	C103	Subsequent cycles					
Visit Number			102	103	104	105, 106, 107...	779	501	778		
Day of cycle			Day 1 of each cycle				Last dose + ≤15 days	Last dose + 28 days			
Study Evaluation Completion	D	7.1.6.1.						X			
Survival Follow Up	D	7.1.6.2.							X		
Antineoplastic therapies since discontinuation of study treatment	D	5.						X			X

Visit assessment window is defined as +/- 3 days except for on-study imaging assessment: +/- 1 week.

\*Once the patient starts the Extension Phase those indicated will not be performed as part of the main study phase, refer to Table 7-3 for all that will be performed in the Extension Phase.

\*\*Survival Follow-up will only be collected until 24 Months post LPFV (date of OS data cutoff).

**Table 7-3 Visit evaluation schedule (Extension Phase)**

	Category	Reference to Section	Visits (every 12 weeks ±1 week)		End of treatment (EoT) for extension	28 Day Safety Follow up	Study Evaluation Completion
Visit Number			EXT Visit 1	EXT Visit 2, EXT Visit 3,	780	501	778
Day of visit			Day 1 of each visit		Last dose + ≤15 days	Last dose + 28 days	
Re-consent	S	7.1.4.	X				
Adverse events	D	7.2.2.	X	Continuous during the study, up to 28 days after the last treatment			
Everolimus administration	D	6.1.	X	Daily dosing			
Letrozole administration	D	6.1.	X if current treatment prior to entry in extension	Daily dosing			
Exemestane administration	D	6.1.	X if current treatment prior to entry in extension	Daily dosing			
Confirmation of Clinical Benefit from investigator	D	7.1.4.	X	At every visit			
Antineoplastic therapies since discontinuation of study treatment	D	7.1.5.				X	
Study Evaluation Completion	D	7.1.6.1.					X
Hepatitis monitoring (if applicable)	S	7.2.2.5.4. 7.2.2.5.5.	As clinically indicated				

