#### **7.1.4 Extension Phase**

Following the overall survival cut-off (24 months post LPFV) and approval of Amendment 5, patients continuing to derive benefit from everolimus will be transitioned to an Extension Phase until disease progression or any other reason for which the patient may be discontinued (refer to [Section 7.1.5](#)).

Patients will be re-consented prior to starting the Extension Phase.

Patients must return to the study center on a quarterly basis (12 weeks  $\pm$  1 week) for resupply of medication at which time drug dispensing information and adverse event information will be collected.

A complete schedule of evaluations required for the Extension Phase is provided in [Table 7-3](#).

The procedures for patients entering the Extension Phase will proceed as follows:

- Safety laboratory assessments: chemistry, hematology, urinalysis, coagulation will be done as clinically indicated
- HBV and HCV testing and monitoring should be continued only for those patients identified during enrollment on first line treatment. Testing should be performed as per [Section 6.2.2.3](#).
- Treatment with everolimus and letrozole (1st line) or everolimus and exemestane (2nd line) until lack of clinical benefit as assessed by Investigator at the site or any other reason for which the patient may be discontinued (refer to [Section 7.1.5](#)) Patients entering the Extension Phase on 1st line treatment and deemed to no longer be clinically benefiting will not be offered 2nd line treatment in the context of this study)
- At every quarterly visit, the investigator is required to confirm that the patient continues to have clinical benefit and may continue receiving study treatment. Although formal assessment of efficacy is not required during the Extension Phase, confirmation of continued treatment benefit as per standard of care is mandatory.
- When patients discontinue the first or second line treatment for any reason, an end of treatment visit following discontinuation of the medication will be performed. The 28 day follow up visit will also be performed to check on continuing AEs/SAEs or any new AEs/SAEs that may have occurred

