### 7.2.2.5 Laboratory evaluations

**Table 7-6 Local clinical laboratory parameters collection plan**

Test Category	Test Name
Hematology	Hematocrit, Hemoglobin, Platelets, Red blood cells, White blood cells, RBC Morphology with Differential (Basophils, Eosinophils, Lymphocytes, Monocytes, Neutrophils)
Chemistry	Albumin, Alkaline phosphatase, ALT (SGPT), AST (SGOT), Bicarbonate, Calcium, Chloride, Creatinine, Creatine kinase, Direct Bilirubin, Indirect Bilirubin, Total Bilirubin, Total Cholesterol, LDL, HDL, Total Protein, Triglycerides, Blood Urea Nitrogen (BUN) or Urea, Uric Acid, Sodium, Potassium, Glucose, Phosphorous
Urinalysis	Standard Dipstick: Bilirubin, Blood, Glucose, Ketones, Leukocytes, pH, Protein, Specific Gravity
Coagulation	Prothrombin time (PT) or International normalized ratio [INR]), Partial thromboplastin time (PTT)
Hepatitis markers	HBV-DNA, HbsAg, HbsAb, HbcAb, HCV RNA-PCR

The standard clinical laboratory analyses described below are to be performed by the local laboratory according to the Visit Schedule. All attempts should be made to obtain scheduled laboratory evaluations  $\leq$  48 hours of the specified time periods, whether or not study treatment is administered. More frequent examinations may be performed at the investigator's discretion if medically indicated; results should be recorded in the eCRFs. Laboratory evaluation that may be performed during the Extension Phase will not be collected in the eCRF.

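### Table 7-3 leaves Extension Phase hepatitis monitoring to clinical indication, while Section 7.1.4 and the row's own references keep HBV-DNA and HCV testing at stated intervals

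*Protocol*

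**What the plan says.** Table 7-3 of the Protocol has a row beginning "Hepatitis monitoring (if applicable", with references to Sections 7.2.2.5.4 and 7.2.2.5.5. Its timing entry is "As clinically indicated".

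Section 7.1.4 treats laboratory work in the Extension Phase in two separate bullets:

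- Safety laboratory tests: "chemistry, hematology, urinalysis, coagulation will be done as clinically indicated".
- Hepatitis: "HBV and HCV testing and monitoring should be continued only for those patients identified during enrollment on first line treatment". The next sentence sends the testing to Section 6.2.2.3.

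Section 6.2.2.3, with Table 6-6, gives the intervals: HBV-DNA about every 4-8 weeks for patients positive for HBV-DNA or HBsAg (who receive prophylaxis), HBV-DNA about every 3-4 weeks for patients negative for both but with qualifying antibodies (no prophylaxis), and HCV every 4-8 weeks. Section 6.2.2.6 asks for frequent HBV-DNA monitoring for as long as everolimus is given.

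Several places send the reader to the schedule table for timing. Section 7.1.4 says "A complete schedule of evaluations required for the Extension Phase is provided in" Table 7-3. The footnote to Table 7-2 says "refer to Table 7-3 for all that will be performed in the Extension Phase". Section 7.2.2.5 says the standard laboratory analyses "are to be performed by the local laboratory according to the Visit Schedule".

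**The concern.** A site that works from the Table 7-3 cell tests for hepatitis only when something clinical prompts it. A site that works from Section 7.1.4 tests every few weeks. The Protocol gives both instructions for the same patients.

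The difference matters because of how the event is defined. Table 6-7 defines HBV reactivation by HBV-DNA, with or without symptoms, and requires antiviral treatment and interruption of the drug when it occurs. A trigger that waits for clinical signs can miss an event that may have none. The most exposed patients are those negative for HBV-DNA and HBsAg but antibody-positive: Table 6-6 gives them no prophylaxis, and their reactivation is simply the first measurable HBV-DNA.

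The indirect safeguard is also weaker than in the Core Phase. There, chemistry (including ALT) is drawn on day 1 of every 28-day cycle. In the Extension Phase it is drawn only on clinical indication, so under the cell neither viral load nor ALT is scheduled. An HCV flare, which calls for stopping study treatment, is defined in Table 6-8 by HCV-RNA and ALT together.

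Omitted tests would be hard to see centrally: "Laboratory evaluation that may be performed during the Extension Phase will not be collected in the eCRF". They would show only in source documents.

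**Working it through.** The Protocol states no figure to reproduce here, so the check is a comparison of texts plus simple interval arithmetic.

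**Side by side**

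| Source | Rule for hepatitis monitoring in the Extension Phase |
|---|---|
| Table 7-3 cell | On clinical indication; no interval |
| Section 7.1.4 | Continue in patients identified at enrollment, per Section 6.2.2.3 |
| Section 7.2.2.5.4 (cited in the row) | During treatment, per Table 6-6; no Extension exception |
| Section 7.2.2.5.5 (cited in the row) | Per the visit schedule, with a pointer to Section 6.2.2.3 |
| Section 6.2.2.6 | HBV-DNA frequently, for the whole of everolimus therapy |

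The words in brackets in the row label limit who is monitored, not when, so they do not reconcile the cell with Section 7.1.4. That section applies the clinical-indication phrase only to chemistry, hematology, urinalysis and coagulation, and then gives hepatitis its own rule. The table attaches the first bullet's phrase to the second bullet's test. For HCV, Section 7.2.2.5.5 is partly circular: in this phase the visit schedule is Table 7-3, so it names two sources that disagree.

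**Intervals in days**

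- HBV-DNA, no prophylaxis: 3 × 7 to 4 × 7 = 21-28 days.
- HBV-DNA, with prophylaxis: 4 × 7 to 8 × 7 = 28-56 days.
- HCV: 28-56 days.
- Table 7-3 cell: none.

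**Visit spacing against those intervals**

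- Core Phase: 28 days, which lies within 21-28 and within 28-56 (before the ±3-day visit window).
- Extension Phase: 12 × 7 = 84 days (±7).
- Ratios: 84/56 = 1.5; 84/28 = 3; 84/21 = 4.

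In one 12-week gap, Section 6.2.2.3 implies 12/4 to 12/3 = 3 to 4 HBV-DNA tests without prophylaxis, and 12/8 to 12/4 = 1.5 to 3 tests for the other two groups. The cell requires none unless clinically prompted. The ratios describe visit spacing; the cell does not itself set a 12-week test interval. No count of missed tests can be given.

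**How many patients**

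Amendment 5 reports 64 patients on first line and 19 on second line at 17-Jun-2016: 64 + 19 = 83. That is an approximate ceiling on all Extension entrants. The hepatitis-positive subset is not stated.

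**The case against.** The strongest reply is that the governing text already gets it right. Section 7.1.4 is the specific section for this phase, the row cites two sections that lead to the intervals, and Section 7.2.2.5.5 itself points to Section 6.2.2.3. Harm needs a site to read one cell and ignore the rest. Moreover, no schedule table carries hepatitis intervals: Table 7-1 shows the test at screening only, and Table 7-2 is blank in the text available (either could be a loss in PDF conversion). The intervals are approximate and framed as recommendations. Patients will have been enrolled for about two years, so sites should know their hepatitis status. A detected HBV reactivation would still be recorded as a grade 3 or 4 adverse event.

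Most of this stands as a limit on weight. A site that follows Section 7.1.4 does the right thing, calling the intervals fixed is slightly strong, and few patients are likely to be affected. The Table 7-2 footnote chiefly explains which Core Phase visits stop at Extension entry and does not by itself make the table override the text.

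It does not remove the contradiction. A blank or screening-only row leaves the text rule unopposed, whereas the Table 7-3 cell states a different rule. Adverse event reporting captures only reactivations that someone has tested for.

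**Conclusion.** The point holds. The Table 7-3 cell contradicts Section 7.1.4 and the sections the row cites, and the conflict is in the current text. It replaces intervals of about 21-28 or 28-56 days with no interval, for up to 3 years, in a phase where visits are 84 days apart.

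This is a patient-safety inconsistency that should be corrected. It does not affect the primary endpoint, any efficacy analysis or the sample size. Its practical weight rests on two things the Protocol does not tell us: how many Extension patients needed hepatitis monitoring (probably few) and how many sites would work from the table rather than the text.

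A minor related wording point: Section 7.2.2.5.5 limits HCV follow-up to patients with a history of hepatitis C, while Sections 6.2.2.3 and 7.1.1.4 also include those RNA-positive at baseline.

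**What to change.** Change the Table 7-3 cell to: *per Section 6.2.2.3 / Table 6-6 for patients identified at enrollment, between visits if needed*.

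As a minor alignment, change the condition in Section 7.2.2.5.5 to: *has a history of Hepatitis C or is HCV RNA-positive at baseline*.

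The cost is one table cell and one clause. No test is added beyond what Section 7.1.4 already asks for. Some samples will fall between the 12-weekly visits, and Table 7-6 already places hepatitis markers in the local laboratory plan.
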